4.3 Pharmacokinetic Analysis Population

Subjects in the safety population who have at least one (1) measurable post-EQ001 exposure concentration will be included in the PK analysis population.

Statistical Analysis Plan

Sponsor Name: Equilibrium Inc.

Sponsor Protocol ID: EQ001-aGVHD-001

Statistical Analysis Plan

Sponsor Name: Environim Inc

[figure not shown]
[figure not shown]
Statistical Analysis Plan

Statistical Analysis Plan

Statistical Analysis Plan

Sponsor Name: Equillium Inc.

Sponsor Protocol ID: EQ001-aGVHD-001

Statistical Analysis Plan

Sponsor Name: Equillium Inc.

Sponsor Protocol ID: EQ001-aGVHD-001

6. Statistical Methods

6.1 General Principles

All data summary tables, listings and figures will be produced using the SAS® software Version 9.4 or higher.

Analysis Data Model (ADaM) datasets will be prepared using Clinical Data Interchange Standards Consortium (CDISC) ADaM Version 2.1, and CDISC ADaM Implementation Guide Version 1.1. Pinnacle 21 Community Validator Version 2.2.0 will be utilized to ensure compliance with CDISC standards.

Statistical Analysis Plan

Sponsor Name: Equillium Inc.

Sponsor Protocol ID: EQ001-aGVHD-001

Statistical Analysis Plan

Sponsor Name: Equillium Inc.

Sponsor Protocol ID: EQ001-aGVHD-001

6.1.1 Definition of Baseline and Change from Baseline

Baseline value of a parameter is defined as the last non-missing measurement prior to first dose of study treatment, including unscheduled readings (see Section 6.1.2 for definitions of unscheduled readings).

Change from baseline will be calculated by subtracting the baseline value from the value at the timepoint of interest.

6.1.2 Repeat and Unscheduled Readings

All assessments not performed at scheduled timepoints (e.g., clinical laboratory assessments) are considered unscheduled assessments. Unscheduled measurements will be labelled as 'Unscheduled' in the listings. Data from unscheduled assessments will not be included in the by-visit data summaries except for clinical activity data summaries.

6.2 Subject Disposition

Subject disposition data will be summarized and will include number and percent of subjects on study, completed the study, discontinued the study prematurely by the primary reason for discontinuation. Similar disposition table will also be created summarizing the treatment completion status. This table will include subjects on treatment, completed treatment, and withdrew study treatment by the primary reason for withdrawal of study treatment in the number of subjects and percentage format. Subject enrollment by study site and important protocol deviations will also be summarized.

6.3 Demographics and Baseline Characteristics

Demographics and other baseline characteristics will be summarized. These include age, sex, race, ethnicity, weight and height. Baseline disease and graft characteristics data include primary disease resulting in transplant, time from graft to onset of GVHD, organ involvement (skin only, GI (upper and/or lower) only, liver only, ≥ 2 organs), aGVHD clinical grade, donor's age, sex and relationship, graft source, HLA matching status, conditioning regimen, and aGVHD prophylaxis regimen(s). If data are available, Ann-Arbor risk classification score at baseline

Statistical Analysis Plan

Sponsor Name: Equillium Inc.

Sponsor Protocol ID: EQ001-aGVHD-001

based on the MAGIC algorithm will also be categorically summarized for subjects with a clinical diagnosis of aGVHD grade II at baseline.

6.4 Medical History

Medical history will be coded using the Medical Dictionary for Regulatory Activities (MedDRA) Version 21.1 (or a later version if updated during the study). All medical history data will be listed, and the number and percentage of subjects with any medical history will be summarized by system organ class (SOC) and preferred term (PT).

6.5 Prior and Concomitant Medications

Medications received prior to or after the first study treatment will be coded using the WHO Drug Dictionary, Version 092018 Enhanced Dictionary Version B3 format (or a later version if updated during the study), Anatomical Therapeutic Chemical (ATC) Classification codes.

Prior medications and concomitant medications are defined as follows:

- Prior medications are those taken prior to the first dose date of study treatment.
- Concomitant medications are those with a start date on or after the first dose date of study treatment, or those with a start date before the first dose date of study treatment and a stop date on or after the first dose date of study treatment or ongoing at the end of study.

A medication can be a prior medication and a concomitant medication at the same time if it starts before first dose date and continues on or after the first dose date.

If a medication cannot be classified as "prior" or "concomitant" due to missing or partial date information, it will be classified as concomitant.

Subject incidence of prior and concomitant medications will be summarized by therapeutic class (ATC Level 2) and chemical subgroup (ATC Level 4) within therapeutic class.

Prior medications and concomitant medications will be listed. This listing will include reported term of the medication, therapeutic class, chemical subgroup within the therapeutic class, start and stop dates and indication.

6.6 Exposure to Study Treatment

An overall summary of exposure to study treatment will be presented. This summary will include:

- Number and percentage of subjects who received 1 dose, 2 doses, ..., 5 doses of study treatments.

Statistical Analysis Plan

Sponsor Name: Equillium Inc.

Sponsor Protocol ID: EQ001-aGVHD-001

- Descriptive summary (n, mean, median, SD, minimum, maximum) of number of doses of study treatment.

6.7 Pharmacokinetic Assessment

6.7.1 Statistical Analysis of Pharmacokinetic Variables for Part A

All PK data analyses and summaries will use the PK population. Description of the methods of calculations of PK parameters is not part of this SAP; PK parameter calculations may be done elsewhere. However, descriptive summaries and listings of the raw data (serum concentrations) may be produced based on the availability of the data.

6.9 Clinical Activity

6.9.1 Response to therapy (CR, VGPR, PR, NR, and PD)

At each assessment visit, overall response to therapy will be recorded as complete response (CR), very good partial response (VGPR), partial response (PR), no response (NR), or progressive disease (PD) by the investigator.

Number and percent of subjects with a complete or near complete response (i.e., CR or VGPR) and with any response (i.e., CR, VGPR or PR) will be presented along with 90% exact confidence intervals by assessment visit. If a subject ended treatment prior to an assessment visit that follows immediately after ending treatment, last observed response will be carried forward if the disease assessment was not performed at that visit. However, if the assessment was done but after receiving new aGVHD treatment(s), response will be considered as PD. Disease assessments done after receiving new aGVHD treatments will not be included in summary tables. A bar chart of percent of responders by cohort and visit will be generated. Best overall response (BOR) during the study will also be summarized by BOR category (CR, VGPR, PR, NR and PD). In evaluating BOR for a subject during the study, the hierarchy CR>VGPR>PR>NR>PD will be used where the symbol ' > ' indicating 'better than'. For example, if a subject has a response of NR

[figure not shown]
Statistical Analysis Plan

Sponsor Name: Equillium Inc.

Sponsor Protocol ID: EQ001-aGVHD-001

at Days 15 and 29, VGPR at Day 43, and later progressed (PD), BOR will be VGPR for that subject. A bar chart will also be constructed to graphically display the BOR data.

Further, Day 29 response will be summarized by GVHD clinical grade at screening, worst clinical grade observed on or prior to Day 29 and by categorical grade change (grade worsened, no change, grade improved) from baseline to latest available grade on or prior to Day 29. Additionally, to assess the durability of response seen at Day 29, for subjects with an objective response (i.e., PR or better) at Day 29, disease assessment data will be summarized at assessments done at visits following Day 29.

6.9.2 Progression-free Survival

Progression-free survival (PFS) is defined as the time (days) from the date of first dose of study treatment to the earliest observation of disease progression, relapse of underlying malignancy or death. For subjects not meeting the criteria for a PFS event will be considered censored and PFS will be calculated using the last response assessment date (not the last known alive date). PFS in days will be calculated as:

$$(\text{PFS event date or censoring date} - \text{first dose date} + 1)$$

Number and percentage of subjects with events further broken down by event type (disease progression, relapse of underlying malignancy or death) will be summarized. In addition, Kaplan-Meier (KM) method will be used to estimate the survival distribution function of PFS and the median (80% confidence interval). First and third quartiles of PFS will also be presented. Estimated survival distribution function of PFS will be plotted using the data from all cohorts.

Statistical Analysis Plan

Sponsor Name: Equillium Inc.

Sponsor Protocol ID: EQ001-aGVHD-001

6.9.3 aGVHD-AI (change from baseline)

aGVHD-AI total index score ranges from 0 to 100 with high scores indicating more severe disease activity. The total index score and change from baseline will be summarized by assessment visit.

6.9.4 Organ Stages

Skin, gastrointestinal tract (upper and lower) and liver are the principal organs involved in the diagnosis of aGVHD. As outlined in an appendix in the protocol, each organ is assigned a stage score (0-4) by the investigator based on severity of disease associated with that organ, with a score of 0 reflecting no organ involvement or normal organ function and a score of 5 reflecting most severe disease. Each organ stage and categorical change from baseline over time (improvement by at least one point, no change, worsening by at least one point) will be summarized by assessment visit.

6.9.5 aGVHD Overall Clinical Grade

An overall aGVHD clinical grade (0, I, II, III or IV) will be assigned by the investigator based on the organ stages at the time of assessment with Grade 0 indicating no disease and Grade IV indicating most severe disease. aGVHD overall clinical grade and categorical changes from baseline over time (improvement by at least one grade, no grade change, worsening by at least one grade) will be summarized by assessment visit.

6.9.6 Overall Survival

Overall survival (OS) is defined as time from first dose to death from any cause. For subjects who are alive at the time of analysis, OS will be calculated as the time from first dose to last known alive date and will be considered as censored. OS in days will be calculated as:

$$(\text{Death date or censoring date} - \text{first dose date} + 1)$$

OS data will be summarized similar to PFS data.

In addition to the safety population, this analysis will also be conducted using the evaluable population, the safety population for subjects with ≤ 3 day of systemic steroid dosing prior to dosing of study medication, and the safety population for subjects with > 3 day of systemic steroid dosing prior to dosing of study medication.

6.9.7 Corticosteroid Usage

Initial induction dose of systemically administered corticosteroids is 2 mg/kg/day of prednisone (or equivalent), and this dose should be maintained until disease stabilization is achieved for a duration of 1 week. Total corticosteroid dose administered through Day 29 by Day 29 response will be summarized. eCRF forms

Statistical Analysis Plan

Sponsor Name: Equillium Inc.

Sponsor Protocol ID: EQ001-aGVHD-001

only capture the daily total dose administered, not the daily dosing regimen. For subjects belonging to each response category, total dose administered through Day 29 will be calculated and summarized

Total dose is then the sum of the individual daily doses after converting to the dose to the prednisone equivalent dose. If a subject took multiple medications or had multiple doses of the same medication recorded where the end date of a previous medication/dose coincides with the start date of the next medication/dose, then it will be assumed that subjects did not take the previous medication/dose on the coincident date and started the next dose on that date (i.e. the end date of the previous medication/dose will be set to the end date of that medication/dose - 1). If the subject has a missing end date and the medication/dose is marked as ongoing, then the end date of that medication/dose will be set to the last date known alive or, if the subject died, to the death date -1.

In addition, total dose administered through the earliest time showing an objective response will be summarized for subjects with a response of PR or better. Average daily dose administered (mg/kg) will be calculated by dividing the total dose administered by (subjects baseline weight x number of days until the earliest time showing an objective response) and summarized. Of those subjects who showed an objective response, the number and percentage of subjects discontinued corticosteroid dosing prior to showing an objective response (PR or better) will also be displayed.

Total dose administered through the earliest time showing disease progression, disease relapse or death will also be summarized similarly.

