5.3. Treatment(s) Administered

All subjects will receive standard treatment for aGVHD with systemically administered corticosteroids. All subjects must receive their first dose of study drug within 72 hours (3 days) of the subject's initial systemically administered corticosteroid dose.

The systemically administered corticosteroid treatment will be prednisone, at approximately 1-2 mg/kg/day (or its equivalent) at the time of first dose of study drug administration:

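### The SAP's steroid date rule deletes a one-day steroid record when the next record starts on the same date

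*SAP*

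**What the plan says.** SAP 6.9.7 (Corticosteroid Usage) sums daily doses after conversion to prednisone equivalents. It reports totals through Day 29 by Day 29 response, through first objective response, and through progression, relapse or death.

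Overlapping dates are handled by one rule. Its scope is wide: "If a subject took multiple medications or had multiple doses of the same medication recorded". It applies where "the end date of a previous medication/dose coincides with the start date of the next medication/dose". Its stated premise is that "it will be assumed that subjects did not take the previous medication/dose on the coincident date and started the next dose on that date". The resulting adjustment is that "the end date of the previous medication/dose will be set to the end date of that medication/dose - 1". The section also says that the case report forms "only capture the daily total dose administered, not the daily dosing regimen".

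For responders, "total dose administered through the earliest time showing an objective response will be summarized for subjects with a response of PR or better". The average daily dose is then obtained by "dividing the total dose administered by (subjects baseline weight x number of days until the earliest time showing an objective response". The section gives no start day for either the dose sum or the day count.

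Steroids begin before study drug. Protocol 5.3 says: "All subjects must receive their first dose of study drug within 72 hours (3 days" of the initial systemic steroid dose. SAP 6.9.6 and 6.9.9 also plan a subgroup with more than 3 days of systemic steroid before study drug.

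**The concern.** The rule is meant to stop a changeover day being counted twice. For a record lasting several days it does that. For a record that starts and ends on the shared date there is no earlier day to fall back on. The adjustment places the end before the start, and a recorded administration is treated as if it never happened.

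Corticosteroid usage is a listed clinical activity endpoint (SAP 3.1). Each total in 6.9.7, and the average built from it, inherits the loss for any subject with such a record.

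A lesser gap concerns the average daily dose. Both parts of the ratio end at first response. However, the start day is unstated, and *through* for the dose against *until* for the days leaves open whether the response day counts. Because steroids can precede Day 1, two programmers could derive different averages from the same data.

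**Working it through.** The plan states no figure on this point, so there is none to reproduce. The rule was applied as written to assumed records. Doses, record patterns and response days below are illustrations, not values from the plan.

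**Date rule.** Days in a record = end − start + 1. If the end of one record equals the start of the next, the earlier end is reduced by 1. Totals run from Day 1 through Day 29.

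| Assumed records (mg/kg/day) | Without the rule | With the SAP rule | Effect |
|---|---|---|---|
| 2 on Days 1–7, then 1 on Days 7–29 | 7×2 + 23×1 = 37 | 6×2 + 23×1 = 35 | Shared day counted once, as intended |
| 2 on Day 1 only, with 1 on Days 1–29 | 1×2 + 29×1 = 31 | 0×2 + 29×1 = 29 | One-day record lost |
| 2 on Day 1 only, then 1 on Days 2–29 | 1×2 + 28×1 = 30 | 30 | Rule not triggered, record kept |

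In the second row the length is (d − 1) − d + 1 = 0 days. If both doses were given, the shortfall is (31 − 29)/31 = 2/31 = 6.5%.

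The size depends on the assumed doses. Let the lost record be p mg/kg and the remaining course c mg/kg/day for D days. The share lost is p/(p + c×D), provided both doses were taken:

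- D = 29: from 1/(1 + 2×29) = 1.7% to 2/(2 + 1×29) = 6.5%.
- D = 15: from 1/(1 + 2×15) = 3.2% to 2/(2 + 1×15) = 11.8%.

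The truth behind the second row's records could differ. If the longer record really began on Day 2, the true total is 30: the SAP gives 29, and keeping both records gives 31. If the one-day entry was not a separate administration, the true total is 29 and the SAP is right.

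**Average daily dose.** Assume a constant 2 mg/kg/day, k steroid days before Day 1, and first response on Day R. The dose sum may cover R or R + k days. The day count may be R − 1, R or R + k. For k = 3:

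| R | Lowest: 2R/(R + 3) | Highest: 2(R + 3)/(R − 1) |
|---|---|---|
| 8 | 16/11 = 1.45 | 22/7 = 3.14 |
| 15 | 30/18 = 1.67 | 36/14 = 2.57 |
| 29 | 58/32 = 1.81 | 64/28 = 2.29 |

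With k = 0 and R = 15, only the counting convention matters: 30/15 = 2.00 or 30/14 = 2.14. With the same start day and an inclusive count in both parts, every case returns exactly 2.00.

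**The case against.** The strongest reply is that the rule is an openly stated imputation that works for the ordinary multi-day changeover. Because the forms hold a daily total, two entries on one date need not mean two administrations. That stands, and it is why the loss is conditional on both doses having been given. It does not rescue the one-day case, where the rule deletes a recorded dose without any check.

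A reader might infer more than the text supports:

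- *Every one-day record is erased.* No. The next record must start on that same date. A one-day dose given during a course that began earlier does not by itself trigger the rule.
- *The error is always downward, towards apparent steroid sparing.* No. If the next dose is the higher one and the subject took only the earlier, lower dose that day, the rule over-counts. The summaries concern an open-label part with no control arm. The between-group steroid comparison in Protocol 9.9 belongs to Part B, which the available SAP text does not cover.
- *The average's dose window and day count are unrelated.* No. Read with the preceding sentence, they share an end point. The SAP does not say that doses before Day 1 enter the total while days are counted from Day 1, and a mismatch could run either way.

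SAP text between sections 4.3 and 6 is unavailable and may hold date conventions. PFS and OS have explicit formulas (first dose date as origin, plus 1), but nothing visible extends them to the steroid average.

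**Conclusion.** The point holds in a narrow form. As written, SAP 6.9.7 gives zero days to a one-day steroid record whose date equals the start of the next record, so its dose is lost. In the worked example the Day 29 total falls by 6.5%. Over the assumed doses the range is 1.7% to 6.5% at Day 29 and 3.2% to 11.8% at Day 15, per affected subject and only if both doses were given. The documents do not give the number of such records, so the effect on any cohort summary cannot be stated.

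The average daily dose needs clarification and is not shown to be wrong. Its start day and counting convention are not visible, and the 1.67 to 2.57 range around a true 2.00 at Day 15 combines the most unfavourable choices with three pre-dose steroid days.

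Both matters affect descriptive Part A output. No sample size, error rate or escalation rule depends on them. This is a minor correction worth making before programming.

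**What to change.** In SAP 6.9.7, apply the one-day set-back only when the earlier record starts before the shared date. When the earlier record's start and end dates are equal, keep it and add its prednisone equivalent for that day. Query same-drug entries on one date, because the form is meant to hold a daily total.

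As a secondary clarification, define the average daily dose over one named start day through the response day inclusive, and use that window for both the dose sum and the day count.

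The cost is about two sentences and a small derivation change, plus some data queries. The downside is that an occasional duplicate entry, or a changeover recorded a day early, may be over-counted: in the example, 31 mg/kg where the true total was 29 or 30.

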6.9.8 Chronic GVHD

Number and percentage of subjects developing chronic GVHD (cGVHD) will be presented by visit and during anytime during the study. If data permits, time from first study treatment to developing cGVHD will be summarized using KM method analogous to PFS.

Statistical Analysis Plan

Sponsor Name: Equillium Inc.

Sponsor Protocol ID: EQ001-aGVHD-001

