1. INTRODUCTION

1.1. Background

Hematopoietic stem cell transplantation (HSCT) is a potentially curative treatment for both benign and malignant hematologic conditions. Unfortunately, graft versus host disease (GVHD), a syndrome in which donor cells recognize and attack host tissues, remains a major cause of morbidity and mortality following HSCT. GVHD is a systemic inflammatory condition primarily mediated by the transplanted immune system that can lead to severe multi-organ damage. The need for increased and prolonged immunosuppression to treat GVHD, in addition to the immunosuppressive effects of the disease itself, results in poor quality of life for these patients and increases the risk of infection, organ impairment, and death.

Despite prophylactic treatment, acute GVHD (aGVHD) affects 30 to 70% of HSCT recipients, and chronic GVHD (cGVHD) occurs in 20 to 50% of HSCT recipients depending on the type of transplant, patient characteristics, and GVHD prophylaxis regimen [REDACTED]

[REDACTED] Historically, aGVHD has been defined as a constellation of signs and symptoms occurring in the first 100 days following HSCT, while cGVHD referred to a somewhat different constellation of signs and symptoms occurring after 100 days. However, a clear distinction between the 2 conditions has been challenged by the recognition of typical signs of aGVHD and cGVHD outside of these delineated periods [REDACTED]

[REDACTED] In 2014, the National Institutes of Health released new consensus criteria that refined the definitions of both acute and chronic GVHD, addressing issues of controversies in the overlap between the 2 conditions [REDACTED] Although aGVHD and cGVHD involve distinct pathological processes (aGVHD has a strong inflammatory component, whereas cGVHD displays more autoimmune and fibrotic features), CD4+ T helper 17 (Th17) cells play a critical role in the pathogenesis of both forms.

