3.1 Clinical Activity Endpoints

- Response to therapy (Complete response [CR], Very Good Partial Response [VGPR], Partial response [PR], No response [NR], and Progressive disease [PD])
- Progression-free survival (PFS)

Statistical Analysis Plan

Sponsor Name: Equillium Inc.

Sponsor Protocol ID: EQ001-aGVHD-001

- aGVHD activity index (aGVHD-AI) and change from baseline
- Organ stages and change from baseline
- aGVHD overall clinical grade and change from baseline
- Overall survival (OS) – Time from first dose to death from any cause
- Relapse incidence and non-relapse mortality
- Corticosteroid usage
- Subjects who discontinued corticosteroids
- Disease status (disease relapse or chronic GVHD (cGVHD)) during long-term follow-up period

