6.10.5 Relapse of Underlying Malignancy and Death

Number and percentage of subjects whose underlying malignancy relapsed or died will be summarized for the following categories:

- Malignancy relapsed by Day 29
- Death by Day 29
- Death by Day 29 with no relapse of malignancy
- Malignancy relapsed during the study
- Death during study with no relapse of malignancy
- Death during study after relapse of malignancy

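### SAP 6.9.8 summarises time to cGVHD by Kaplan-Meier on the model of PFS, and no reading of that cross-reference gives a sound estimate of cGVHD incidence (minor, descriptive summary)

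*SAP*

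**What the plan says.** SAP 6.9.8 plans two things for chronic GVHD. The first is the number and percentage of subjects developing it, by visit and at any time. The second, conditional on the data, is that "time from first study treatment to developing cGVHD will be summarized using KM method analogous to PFS". The origin (first study treatment) and the event (developing cGVHD) are clear. The section does not say how death or malignancy relapse without cGVHD is treated, nor which date censors a cGVHD-free subject.

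The section it points to, SAP 6.9.2, has both kinds of rule. PFS ends at "the earliest observation of disease progression, relapse of underlying malignancy or death". For subjects without an event, "PFS will be calculated using the last response assessment date (not the last known alive date". The presentation includes the KM curve and the median, and "First and third quartiles of PFS will also be presented".

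Three other places set the context:
- Protocol 6.9 places the cGVHD assessment at the long-term follow-up visits, and SAP 6.9.9 reports cGVHD status at Days 253 and 337.
- The Protocol synopsis (Safety and Long-Term Follow-Up) has disease progression assessed at Day 169, with phone contacts after that.
- SAP 3.1 lists "Relapse incidence and non-relapse mortality" among the endpoints, and SAP 6.10.5 tabulates "Death during study with no relapse of malignancy".

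**The concern.** A subject who dies without cGVHD can no longer develop it. Kaplan-Meier with that death censored treats the subject as still able to do so, and 1-KM then estimates a quantity for a population in which nobody dies. Deaths before cGVHD are foreseeable here. Protocol 1.1 says that GVHD "remains a major cause of morbidity and mortality following HSCT", the SAP plans to count deaths without relapse, and cGVHD is assessed late, so early deaths will tend to come before recorded cases.

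The reference to PFS does not remove the difficulty, because the PFS rules were written for a different endpoint. What is at stake is a curve and quartiles that could show cGVHD as more frequent or earlier than it was, or that describe a different endpoint from the one named. Two programmers could also produce different curves from the same data.

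**Working it through.** The plan gives no figure for this analysis, so there is nothing to reproduce. Each reading is worked through with illustrative inputs.

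**Inputs from the documents.** Part A has about 24 subjects in dose escalation (Protocol 3.1). cGVHD contacts are at Days 253 and 337 (SAP 6.9.9). The last scheduled progression visit is Day 169 (Protocol synopsis). Protocol 1.1 says that "chronic GVHD (cGVHD) occurs in 20 to 50% of HSCT recipients".

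**Assumptions.** The documents give no rates of death or loss. The 35% cGVHD used below is the middle of the 20 to 50% range. That range refers to HSCT recipients in general with no time window, so applying it to 337 days from first dose in subjects with aGVHD is also an assumption.

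**Reading 1: deaths without cGVHD are censored.** Let C1 be the true cumulative incidence of cGVHD by Day 337 and C2 that of death before cGVHD, with constant hazards. The total cumulative hazard is H = -ln(1 - C1 - C2), the cGVHD part is h1 = H × C1/(C1 + C2), and 1-KM = 1 - exp(-h1).

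For C1 = 0.35 and C2 = 0.20: H = -ln(0.45) = 0.7985; h1 = 0.7985 × 0.35/0.55 = 0.5081; 1-KM = 1 - exp(-0.5081) = 39.8%.

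| Deaths before cGVHD (assumed) | True cGVHD | 1-KM | Excess, points |
|---|---|---|---|
| 0% | 35% | 35.0% | 0 |
| 5% | 35% | 36.0% | 1.0 |
| 10% | 35% | 37.2% | 2.2 |
| 20% | 35% | 39.8% | 4.8 |
| 30% | 35% | 43.2% | 8.2 |

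With 20% deaths, changing the assumed cGVHD to 20% gives an excess of 2.5 points, and changing it to 50% gives 7.7 points.

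The first quartile moves too. By KM it is 337 × (-ln 0.75)/h1 = 337 × 0.2877/0.5081 = Day 191. By cumulative incidence it is 337 × (-ln(1 - 0.25 × 0.55/0.35))/0.7985 = Day 211. These days hold only if cGVHD is dated by diagnosis and arises at a constant rate from Day 1. If it is dated by contact, no event can fall before Day 253.

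The size depends on timing. Take 24 subjects with 5 deaths at Day 120, 3 cGVHD cases at Day 253, 4 at Day 337, and everyone else followed throughout. Then 1-KM = 1 - (16/19) × (12/16) = 36.8%, against a cumulative incidence of 7/24 = 29.2%, an excess of 7.7 points. If all deaths come after the last cGVHD event, both estimates are 29.2% and there is no excess.

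**Reading 2: the PFS event rule is carried over.** Deaths now count as events. In the same 24 subjects the curve reaches (5 + 7)/24 = 50.0%, against 29.2% who developed cGVHD. Any malignancy relapse would add to it. This is a composite of cGVHD, relapse and death, not time to developing cGVHD.

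**Reading 3: the PFS censoring date is carried over.** Censor the 5 deaths at Day 120 and the 12 cGVHD-free survivors at Day 169, and date the cases at Days 253 and 337. The risk set at Day 253 is then the 7 future cases alone: 1-KM = 1 - (4/7) × (0/4) = 100%. This is the extreme case, but it shows the direction. Subjects known to be cGVHD-free at a later contact are dropped before it, while the cases are kept.

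**Do the planned percentages make the curve redundant?** Not when subjects are lost. Take 24 subjects with 5 cases, 2 earlier deaths and 4 lost before Day 253, leaving 18 at risk. The crude percentage is 5/24 = 20.8% and 1-KM is 5/18 = 27.8%. Cumulative incidence is (22/24) × 5/18 = 25.5% if the deaths come before the losses, or (18/20) × 5/18 = 25.0% if the losses come first.

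**Scale.** The exact 90% confidence interval for 5/24 is 8.6 to 38.9%, wider than the excess in any row of the table.

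**The case against.** Four objections deserve an answer.

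- *The SAP does not say that deaths will be censored.* Correct. A reader might infer that 6.9.8 censors deaths, or that it leaves death and censoring without any rule. The documents support neither, because the section refers to PFS, which has both rules. SAP 6.9.6 says OS is summarised like PFS only after stating its own event and censoring date. That hints that the analogy concerns presentation, but 6.9.8 states no such rules of its own, so the hint is weak. The sound criticism is that the cross-reference is ambiguous and fits badly.
- *Overstatement does not follow from every death.* Also correct. A reader might infer that 1-KM is too high whenever someone dies first. It is too high only if a cGVHD event follows a death without cGVHD.
- *A rule may exist in text we cannot see.* SAP Section 5 and parts of the text around 4.3 to 6.1 are missing from this copy. A general censoring or competing-event rule there would narrow the point, so it concerns what 6.9.8 itself says.
- *It hardly matters.* The summary is optional, descriptive and limited to Part A. No test or decision rule in the visible text uses it, and the SAP does not say that 1-KM will be reported as the incidence of cGVHD. All of that stands and sets the weight. It does not rescue the method, since the bias under the first reading runs in one direction and the other two readings change the endpoint or the risk set.

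**Conclusion.** The point holds with minor weight. As written, 6.9.8 leads to one of three results: a KM curve that overstates cGVHD incidence once a case follows a death, a composite labelled as cGVHD, or a risk set that loses cGVHD-free subjects before cGVHD is assessed. The first effect is about 1 to 8 points at 5 to 30% prior deaths and 35% cGVHD under constant hazards. It is zero if no cGVHD event follows a death, and larger if deaths cluster early and cGVHD is recorded late. All of these rates are assumptions. A reader might go on to infer that the trial's reported cGVHD frequency will be wrong. The documents do not support that: the planned numbers and percentages in 6.9.8 and 6.9.9 do not depend on the curve.

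**What to change.** In SAP 6.9.8, replace Kaplan-Meier with the Aalen-Johansen cumulative incidence function and state:

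- **Event:** first recorded cGVHD, dated by diagnosis if that date is collected, otherwise by the contact at which it was recorded.
- **Competing event:** death without cGVHD.
- **Malignancy relapse:** not itself a cGVHD event; say how follow-up after relapse is handled.
- **Censoring:** cGVHD-free survivors at the last contact or visit at which cGVHD status was ascertained, including one before Day 253 for subjects lost early, and not at the PFS last-response-assessment date.
- **Counts:** keep the planned number and percentage.

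The cost is a few lines of SAP text and slightly more programming with a standard SAS option. With cGVHD dated by contact, no new data are needed for subjects who reach the long-term contacts: deaths are reported through Day 337 unless consent is withdrawn (Protocol 7), and cGVHD status is assessed at Days 253 and 337 (SAP 6.9.9). The visible text does not confirm that a diagnosis date or a cGVHD status before Day 253 is collected, so both should be checked against the eCRF.
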